3.2 Primary Endpoints

The overall feasibility of accelerated deep TMS (aTMS) for smoking abstinence: assessed through tolerability (frequency of side effects reported at each visit during Week 1), acceptability (self-reported ratings collected at the end of treatment), retention rate (the proportion of participants who completed the full study), and adherence rate (the proportion of completed sessions among participants who initiated treatment).

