Participants' activities were not systematically controlled during treatment sessions or during the intersession intervals; participants were allowed to do light cognitive activities such as reading or using their computer or smartphone.

On each day of Week 1, the TCQ-SF will be administered twice to measure nicotine craving—once before and once after the aTMS treatment.

Brief counseling for smoking cessation, adapted from the Mayo Clinic's 'Smoke Free and Living It' manual, will be administered at W1D1 and W1D5. The brief counseling sessions may also be offered remotely, based on participant preference and logistical feasibility.

The first day of Week 1 (W1D1)

- Concomitant medication log, recorded by its generic name, dosage, and dosing frequency
- Timeline Follow-Back (TLFB) – Amount of cigarette used every day since the last follow-up
- Tobacco Craving Questionnaire-Short-Form (TCQ-SF), to measure smoking craving. TCQ-SF will be administered twice—once before and once after the aTMS treatment.
- Minnesota Nicotine Withdrawal Scale (MNWS), to measure the nicotine withdrawal symptoms.
- Urine drug panel
- Urine pregnancy test, if required
- Brief counseling for smoking cessation, adapted from the Mayo Clinic's 'Smoke Free and Living It' manual.
- Resting motor threshold measurement
- Accelerated deep TMS treatment
- Adverse event log

The second, third, and fourth days of Week 1 (W1D2, W1D3, W1D4)

- Concomitant medication log, recorded by its generic name, dosage, and dosing frequency
- Timeline Follow-Back (TLFB) – Amount of cigarette used every day since the last follow-up
- Tobacco Craving Questionnaire-Short-Form (TCQ-SF), to measure smoking craving. TCQ-SF will be administered twice—once before and once after the aTMS treatment.
- Minnesota Nicotine Withdrawal Scale (MNWS), to measure the nicotine withdrawal symptoms.

- Accelerated deep TMS treatment
- Adverse event log

The fifth day of Week 1 (W1D5)

At the end of Week 1 (W1D5), a urine cotinine test will be performed, alongside TLFB to determine 7-day point-prevalence abstinence.

At W1D5, for acceptability assessment, a TMS Experience Questionnaire will be administered. Participants will be asked to retrospectively rate (from 1=not at all to 5=very much so) 15 items querying their perceptions of the treatment, its side effects, and its benefits as well as their preferences regarding treatment format and logistics.

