Follow-up period (Week 13 and 26)

During the Week 13 and 26 visit, a urine cotinine test and TLFB will be administered to determine prolonged abstinence and continuous abstinence. Three-month or six-month prolonged abstinence is defined as abstinence from the end of treatment (W1D5) to the end of follow-up (Week 13 or 26), while three-month or six-month continuous abstinence is defined as abstinence from the target quit day (in Week 1) to the end of follow-up (Week 13 or 26). Assessments for nicotine dependence, withdrawal, craving, and symptoms of depression, anxiety, and mania will also be performed.

- Concomitant medication log, recorded by its generic name, dosage, and dosing frequency
- Timeline Follow-Back (TLFB) – Amount of cigarette used every day since the last follow-up
- Fagerstrom Test of Nicotine Dependence (FTND). The FTND is a measure of physical dependence severity.
- Tobacco Craving Questionnaire-Short-Form (TCQ-SF), to measure smoking craving.
- Minnesota Nicotine Withdrawal Scale (MNWS), to measure the nicotine withdrawal symptoms.
- Patient Health Questionnaire (PHQ-9), to track the possible effects of TMS on depression symptoms.

- General Anxiety Disorder-7 (GAD-7), to track the possible effects of TMS on anxiety symptoms.
- Altman Self-Rating Mania Scale (ASRM), to track the possible effects of TMS on developing manic/hypomanic symptoms
- Adverse event log
- Urine cotinine test (threshold: 200 ng/ml)
- Brief counseling for smoking cessation, adapted from the Mayo Clinic's 'Smoke Free and Living It' manual.

All assessments and surveys during research visits can be completed in one of two ways, based on participant preferences or each site's standard data collection practices:

1. **Paper option:** Assessments and surveys printed from REDCap will be completed by hand. A study delegate will review the paper source for completeness and accuracy and enter the data into REDCap.
2. **Electronic:** A study delegate will log into REDCap and will remain present while the participant enters their responses to assessments on an electronic device (e.g., computer, iPad). The study delegate will review the assessment for completeness before saving and help the participant navigate to the next assessment or survey, as necessary.

Procedures for addressing active suicidal ideation during research visits can be found in [Section 8.5 \(Safety Management Plan\)](#).

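### Acceptability, a primary feasibility component, is rated with staff present (electronic route) or under staff accuracy review (paper route), which may encourage favourable answers

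*Protocol*

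**What the plan says.** Section 3.2 of the protocol makes feasibility the primary endpoint, with four components: tolerability, acceptability, retention and adherence. The second is described as "acceptability (self-reported ratings collected at the end of treatment").

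Section 6.1 names the instrument: "At W1D5, for acceptability assessment, a TMS Experience Questionnaire will be administered". It has "15 items querying their perceptions of the treatment, its side effects, and its benefits", together with preferences about format and logistics, each rated from 1 to 5. No other acceptability instrument is named.

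The same section then sets a general rule: "All assessments and surveys during research visits can be completed in one of two ways", the choice being "based on participant preferences or each site's standard data collection practices".

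- **Electronic route:** "A study delegate will log into REDCap and will remain present while the participant enters their responses to assessments on an electronic device". Then, "The study delegate will review the assessment for completeness before saving".
- **Paper route:** the form is filled in by hand. A delegate will then "review the paper source for completeness and accuracy" and key the data into REDCap.

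Sections 3.1 and 5.8 confirm one arm and no blinding.

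**The concern.** The questionnaire asks participants for their opinion of the treatment that the study team has just given them. It is completed at the end of five days of roughly three hours each (section 5.4), on a day that also includes treatment and counselling. People who answer such questions beside a member of the study staff, or who know that staff will read the form, may give kinder answers than they would in private.

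In a randomised comparison, a tendency of that kind would act on both arms and partly cancel. Here there is one arm, so any shift passes directly into the acceptability estimate. Section 3.1 says the pilot is meant to guide a later controlled trial, so that estimate will be used for planning. Analysis cannot remove the effect afterwards, because the conditions of rating are fixed when the data are collected.

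**Working it through.** The protocol gives no mean, standard deviation, target or threshold for acceptability, so there is no figure to reproduce. The check is a reading of the sections against each other, followed by an illustration of scale.

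**1. Does the rule reach this questionnaire?** Yes. The rule in 6.1 covers every assessment and survey at research visits, and the questionnaire is listed at the fifth treatment day. Three other places could have supplied an exemption, and none does:
- Section 8.5 allows some self-report to be done virtually, but adds no privacy from staff.
- Section 13.0 asks for research activities to be held as privately as possible, which concerns the setting and not the presence of study staff.
- Section 12.2 keeps staff with a clinical relationship out of the consent discussion, but nothing similar is written for these ratings.

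**2. What does each route impose?**
- Electronic: presence during entry is stated, and the review is for completeness only.
- Paper: no presence is stated, but the later review covers accuracy as well as completeness. There is no source against which an opinion rated 1 to 5 could be checked for accuracy.

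On both routes a delegate handles answers that can be linked to the participant.

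**3. Who is the delegate?** Section 5.4 assigns stimulation to a technician, nurse or other trained person. Section 6.1 says only that a study delegate supervises or reviews. Whether these are the same people is neither stated nor excluded.

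**4. In which direction would answers move?** Courtesy would raise a benefit item, lower an item on how troublesome side effects were, and have no clear direction on a scheduling preference. The item wording is not given, so no single direction can be assigned to all 15 items.

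**5. What does mixing routes do?** Suppose supervision shifts an item by d points and a fraction f of raters is supervised. The pooled mean then moves by f × d. If the two sites have fractions f1 and f2, their difference carries (f1 − f2) × d. Should one site be wholly supervised and the other not, f1 − f2 = 1 and the site contrast contains all of d.

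**6. Scale, by assumption only.** Assume 30 to 40 raters (the completer and enrolment targets) and an item standard deviation of 1:
- Standard error = 1/√n: 1/√30 = 0.183 and 1/√40 = 0.158.
- 95% half-width = 1.96 × standard error: 0.36 and 0.31.
- An assumed shift of 0.2 points is at least 0.2/0.183 = 1.1 standard errors and lies inside the half-width.
- An assumed shift of 0.5 points is at most 0.5/0.158 = 3.2 standard errors and lies outside it.

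Both the standard deviation and the shifts are assumptions. The illustration shows only that a shift could be small or large relative to the reported interval. It is not evidence that a shift exists.

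**The case against.** The best case for leaving the text alone is that supervised entry is an ordinary completeness control, useful for an instrument given once. The delegate's stated tasks on the electronic route are navigation and completeness, and being present need not mean watching the answers. Handling details could sit in the Data Management Plan or staff training. Retention and adherence count visits and sessions and are untouched by how a questionnaire is supervised. The trial is an exploratory pilot, and no acceptability cut-off is set.

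Much of this stands, and it rules out several stronger readings that a reader might infer:
- *That every rating is given in front of staff.* Presence is stated for the electronic route only.
- *That the treating team does the observing.* The delegate's role in treatment is not given.
- *That ratings are biased upward.* The document supports a risk, not an observed effect, and the direction differs by type of item.
- *That the feasibility conclusion fails.* Acceptability is one component of four, and no decision rule depends on it.

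The objection does not supply a safeguard. The rule in 6.1 applies to this questionnaire as written, and an accuracy review has no evident purpose for opinions. Staff presence may help with safety follow-up of the PHQ-9 (section 8.5), but that reason does not extend to a treatment-experience form when adverse events are logged separately on the same day.

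**Conclusion.** The point holds as a risk that is cheap to remove. A self-report that forms one primary component is collected with staff present on one route and with staff accuracy review on the other. There is no provision for private completion and no comparator to absorb a courtesy effect. The freedom to choose the route by site adds possible confounding of completion conditions with site.

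The size and sign of any bias cannot be derived from the protocol. The consequence is limited to a descriptive acceptability estimate. The conclusion rests on two readings of the text: that the general rule includes this questionnaire, which its wording supports, and that no exemption appears elsewhere in the protocol. A Data Management Plan is cited but not shown. If it already provides private completion, the remaining task is to bring 6.1 into line with it.

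**What to change.** In section 6.1, exempt the TMS Experience Questionnaire from the staff-present rule and from the accuracy review. State that:

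- the participant completes it privately under the study ID, by REDCap survey link or on a paper form placed in a sealed envelope;
- automated prompts for unanswered items replace the staff completeness check on the electronic route;
- the completion mode is recorded, so that ratings can be described by mode and by site;
- participants are told that treating staff will not see their individual answers, and that side effects must therefore also be reported to staff;
- side effects continue to be collected on the adverse event log that day.

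The cost is a short addition to 6.1 and a REDCap survey setting. The downsides are possibly a few unanswered items, particularly on paper, and the need to make clear to participants that the questionnaire does not replace adverse event reporting. The change helps only participants who have not yet reached the fifth treatment day, so it is best made before enrolment.

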6.2 Schedule of Events

Below is the table outlining the assessments, measures, and treatments done at each visit.

	Screening	Baseline	Treatment					Follow-ups				
Week			W1					W3	W5	W9	W13	W26
Visit Code/Number	SC	BL	W1D 1	W1D 2	W1D 3	W1D 4	W1D 5	W3	W5	W9	W13	W26
Assessments & Measures	In-person visit		X	X	X	X	X	X	X	X	X	X
	ICF	X										
	Contact & Demographic Form	X										
	Medical history	X										
	MINI	X										
	TASS	X										
	Smoking Contemplation Ladder	X										
	Quit day plan	X										
	Concomitant Medication Log	X	X					X	X	X	X	X
	Urine Drug Panel		X	X				X				
	Urine Pregnancy Test (if required)			X	X			X				
	TLFB(Cigarettes)		X	X	X	X	X	X	X	X	X	X
	FTND	X	X					X	X	X	X	X
	TCQ-SF (regular or pre-TMS)		X	X	X	X	X	X	X	X	X	X
	TCQ-SF (post-TMS)			X	X	X	X					
	MNSW		X	X	X	X	X	X	X	X	X	X
	PHQ-9		X					X	X	X	X	X
	GAD-7		X					X	X	X	X	X
	ASRM		X					X	X	X	X	X
	AE Log			X	X	X	X	X	X	X	X	X
	Counseling			X				X	X	X	X	X
	Urine cotinine test		X					X	X	X	X	X
	Confirm eligibility			X								
Treat	TMS Experience Questionnaire							X				
	Point Prevalence Abstinence							X	X	X	X	X
	Prolonged Abstinence										X	X
	Continuous Abstinence										X	X
Treat	RMT for TMS			X								
	TMS			X	X	X	X					

7.0 STATISTICAL PLAN

7.1 Sample Size Determination

We aim to assess the abstinence rate at different time points and the feasibility of the accelerated deep TMS protocol for smoking cessation. Based on our previous trial[7], which tested the efficacy of deep TMS as an add-on to varenicline treatment, the point prevalence abstinence rate at Week 12 (8 weeks after the treatment ends) was 82.4% in the varenicline + deep TMS group and 30.7% in the varenicline + sham stimulation group. For this feasibility study, we plan to recruit 30 completers, targeting a sufficient number of completers to allow for meaningful estimates of the abstinence rate across multiple time points. This sample size is consistent with the exploratory nature of a pilot study and will provide valuable preliminary data for planning a larger, fully powered clinical trial in the future.

7.2 Statistical Methods

Descriptive statistics will be used to summarize the baseline clinical and demographic variables for the study population. Subjects with missing values will be compared with completers on baseline characteristics, to help in the understanding of the reasons for missing values, if at least 10 subjects (25%) are found to be missing.

For the abstinence measure, an intent-to-treat (ITT) approach will be used, including all participants who received at least one TMS session, regardless of treatment completion.

Mixed effect logistic regression, using abstinence at the end of treatment, Week 3, Week 5, Week 9, Week 13, and Week 26 as dependent variables will be adjusted to the data. Categorical time points (end of treatment and Week 3, Week 5, Week 9, Week 13 and Week 26) will be specified as fixed effect, and subject intercepts as random effects. Baseline variables correlated with missingness and/or known to be associated with the outcome will be added as covariates, with focus on model parsimony (not to include many covariates) due to small sample size. Abstinence will be analyzed at the end of treatment, Week 3, Week 5, Week 13, and Week 26 as part of our secondary objectives.

Mixed effect models using maximum likelihood estimation accounts for missingness in the dependent variable by using all available information in the estimation, under the MAR assumption (Missing At Random – the values of a data points are not associated with the missing status of the data point after accounting for relevant covariates)[1]. Other measures related to our secondary objectives (e.g., FTND, TLFB, etc.) will also be analyzed using linear mixed or generalized mixed models, depending on the nature of the outcome of interest. Graphs will be used to explore the data, the models assumptions (for example, residual plots), as well as model results (for example, estimated means plot).

Due to small sample, effect sizes with 95% confidence intervals as well as standardized effect sizes will be reported.

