1.4 Clinical Data to Date

In a clinical trial, our group has suggested the efficacy of deep TMS in smoking cessation as an add-on treatment strategy to varenicline (Figure 2)[7].

[figure not shown]

Figure 2. Abstinence rates at Week 4, 12, and 26. Abstinence was measured by 7- day point-prevalence abstinence. All measures were confirmed with plasma cotinine. Bars represent (±) standard error. Group sample sizes: Week 4 (n =18 active, n =16 sham), Week 12 (n =17 active, n =15 sham), and Week 26 (n = 16 active, n =15 sham).; *p<0.05.

In previous aTMS depression studies, the effect of aTMS may be attributed to several factors, including optimized neurocircuit-based targeting, an accelerated treatment schedule, and a higher total pulse count[42–46]. Optimized neurocircuit-based targeting can be achieved through e-field modeling or personalized, connectivity-based biomarkers, such as DLPFC-subgenual anterior cingulate cortex connectivity[42]. The higher total pulse count may also contribute to positive treatment outcomes. For example[47], 90,000 pulses delivered with accelerated protocol (1,800 pulses per session, 10 sessions per day, 5 days per week, over one week) demonstrated better efficacy in treating depression compared to 18,000 pulses administered through a standard protocol (600 pulses per session, 1 session per day, 5 days per week, over 6 weeks). However, the individual components of aTMS still need to be isolated. Many

previous aTMS depression studies combine more than one of these factors. Therefore, even when considering aTMS beyond smoking cessation, isolating the effect of the accelerated treatment schedule is crucial to understand this technique.

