3.3 Secondary Endpoints

1. Proportion of participants achieving 7-day point prevalence abstinence at end of treatment, Week 3, Week 5, Week 9, Week 13, and Week 26.
2. Proportion of participants achieving prolonged and continuous abstinence at Week 13 and Week 26.
3. Change in self-reported craving, average cigarettes smoked per day, and dependence severity (e.g., using standardized questionnaires) from baseline through study completion.

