4.7.4 Participants who are Lost to Follow-up

A patient participant will be considered lost to follow-up if they fail to return for >3 scheduled visits that cannot be rescheduled and are unable to be contacted by the research team.

The following actions will be taken if a participant fails to attend a required study visit:

- The research team will attempt to contact the participant and reschedule the missed visit within the next 4 weeks and reconfirm whether the participant wishes to and/or should continue in the study.

- Before a participant is deemed lost to follow-up, the research team will make every effort to regain contact with the participant (where possible, at least five contact attempts including both telephone calls and emails, unless specific contact preferences were specified by the participant). These contact attempts will be documented in the participant's research record and/or legal health record.
- Should the participant continue to be unreachable, they will be considered to have withdrawn from the clinical trial with a primary reason of lost to follow-up. Data up to the point of their last visit will be included in the analysis.

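### The ITT set for abstinence in Protocol 7.2 is everyone treated, but its only missing-data method covers only those with at least one abstinence outcome and assumes away unseen relapse

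*Protocol*

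**What the plan says.** Section 3.3 defines the first secondary endpoint as "Proportion of participants achieving 7-day point prevalence abstinence at end of treatment" and at Weeks 3, 5, 9, 13 and 26. For abstinence, section 7.2 states that "an intent-to-treat (ITT) approach will be used, including all participants who received at least one TMS session, regardless of treatment completion". Section 3.1 agrees: enrolled people who never start TMS are left out, and all who start are in.

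Section 7.2 then fixes a mixed-effects logistic regression in which the six time points "will be specified as fixed effect, and subject intercepts as random effects". Missing abstinence is dealt with by maximum likelihood, which "accounts for missingness in the dependent variable by using all available information in the estimation, under the MAR assumption". The supporting provisions are a small number of baseline covariates and a descriptive comparison with completers, made only if at least 10 subjects (25%) have missing values.

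All six outcomes come after treatment has begun. The first is at the fifth treatment day: "At the end of Week 1 (W1D5), a urine cotinine test will be performed, alongside TLFB to determine 7-day point-prevalence abstinence". For people lost to follow-up, section 4.7.4 says: "Data up to the point of their last visit will be included in the analysis". No section counts missing as smoking.

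**The concern.** The declared analysis set and the estimation method do not match. A reader who sees an ITT abstinence rate will take its denominator to be all treated participants. The model's denominator is in effect those with at least one recorded abstinence status.

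The second issue is the MAR assumption. Once observed visits and covariates are accounted for, it requires that whether someone is missing does not depend on the status that went unrecorded. In smoking cessation, relapse is itself a plausible reason to stop attending. The protocol says in section 1.0 that relapse remains a challenge, and in section 5.1 that susceptibility is highest early after quitting. A relapse after the last attended visit is never seen.

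No test or threshold depends on abstinence. However, there is no control arm, and section 7.1 justifies the 30 completers as "targeting a sufficient number of completers to allow for meaningful estimates of the abstinence rate across multiple time points". The absolute rate is therefore the efficacy information carried forward.

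**Working it through.** **The plan's own figure.** 40 enrolled for 30 completers: 30 / (1 − 0.25) = 40, and 10 / 40 = 25%, which matches the trigger in 7.2. Some of those 10 may never start TMS and so lie outside the ITT set. Section 7.1 gives no precision target to reproduce.

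**Who is in the fit.** With random intercept u, participant i contributes the integral over u of the product, across observed visits, of p(u)^y × (1 − p(u))^(1 − y). With no observed visit the product is empty, the integral is 1 and the log-likelihood contribution is 0. As a check, the model was fitted with and without such participants. The log-likelihood differed by less than 1e-13 and the estimates by less than 2e-5.

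**Size: no outcome at all.** Let p be the rate among those with an outcome and f the share of treated participants with none, all smoking. The truth is p(1 − f), the model returns p, and the bias is p × f. With p = 30%:
- 1 of 40: 30 × 0.025 = 0.75 points
- 2 of 40: 30 × 0.05 = 1.5 points
- 4 of 40: 30 × 0.10 = 3.0 points

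**Size: loss during follow-up.** The protocol gives no expected loss among treated participants. Two anchors are available. In the earlier trial (section 1.4) the counts start at "Group sample sizes: Week 4 (n =18 active, n =16 sham), Week 12 (n =17 active, n =15 sham") and reach 16 + 15 = 31 at Week 26, so the loss is (34 − 31) / 34 = 8.8%. The plan's own ceiling is 25%.

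The assumptions were true rates of 45, 42, 40, 36, 33 and 30% over the six visits, an intercept SD of 2 or 3, and 60,000 simulated participants per scenario, with the fitted Week 26 probability averaged over the intercept.

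| Assumed dropout | MAR model | Missing = smoking |
|---|---|---|
| Smokers lost more often, total loss 9 to 28% | +0.5 to +2.1 | −0.8 to −5.4 |
| 9% lost, all smoke afterwards | +2.7 to +5.1 | 0 by construction |
| Abstainers lost more often, total loss 8 to 16% | −0.6 to −1.3 | −3.7 to −7.0 |

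Entries are bias in percentage points. In the middle row the lower end applies when the lost are a cross-section of the treated, where p × f again holds: 30 × 0.09 = 2.7. The upper end needs the lost to have been abstinent earlier. For a cross-section, the same formula gives 30 × 0.15 = 4.5 points at 15% loss and 30 × 0.25 = 7.5 at 25%.

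**Against sampling error.** √(0.30 × 0.70 / 40) = 7.2 points; with 35 treated, 7.7 points.

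**At the trial's own size.** In 250 simulated trials of 40, generated from visit-to-visit transitions and fitted with weak penalties, about 27% were missing at Week 26.
- Dropout unrelated to smoking: truth 34.6%, model 37.2% (+2.6), missing = smoking 25.2% (−9.4).
- Dropout 9% per visit in smokers against 1% in abstainers: truth 34.2%, model 37.8% (+3.6), missing = smoking 30.1% (−4.1).
- Dropout 10% against 0%: truth 34.7%, model 39.4% (+4.7), missing = smoking 31.9% (−2.8).

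The +2.6 present without informative dropout reflects model form and small numbers. That leaves 3.6 − 2.6 = 1.0 and 4.7 − 2.6 = 2.1 points for relapse-related dropout, in line with the table.

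**What the added figure would show.** With 9 abstinent among 30 observed (30.0%), the all-treated figure is 9 / 34 = 26.5% if 34 were treated, and 9 / 40 = 22.5% (Wilson 95% CI 12.3 to 37.5%) if all 40 were.

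**The case against.** The strongest reply is that supplementary missing-data analyses normally sit in a SAP, which is not at hand, and that the model itself is kept. The summary table lists descriptive statistics among the methods for abstinence, so crude proportions are not ruled out, and retention is part of the primary endpoint, so loss will be visible. That would answer a complaint about a missing sensitivity analysis. It does not answer the mismatch, because the protocol itself states both the ITT set and a method that does not deliver it.

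Several stronger readings are tempting, and the documents do not support them:

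- A reader might infer that anyone who misses the fifth treatment day is dropped. That is not so: one attended visit at any of Weeks 3 to 26 brings the person into the fit. Section 4.7.3 also asks withdrawing participants to attend an Early Termination Visit with the post-treatment assessments, although 7.2 does not place that visit among its six time points.
- A reader might infer that relapse is ignored. Relapse recorded at an attended visit is used, and earlier visits inform the fit. Only relapse that nobody observed is assumed away.
- A reader might infer very large bias by supposing that those lost had nearly all been abstinent at the end of treatment. Section 5.1 standardises the quit date to the first TMS day, so a 7-day window ending on day 5 normally reaches back before it. Unless the quit date is moved, few can qualify, so the upper end of the 9% range deserves little weight.
- A reader might infer that missing-as-smoking should be the main result. It is too low in every scenario above except universal relapse.

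It also stands that, under the milder patterns, the bias lies within one standard error.

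**Conclusion.** The point holds in limited form. The model in 7.2 covers treated participants with at least one abstinence outcome, not everyone with at least one TMS session. That part follows from the likelihood and needs no assumption.

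The bias from unobserved relapse does rest on assumptions: a Week 26 rate near 30%, an intercept SD of 2 or 3, and the dropout patterns listed. It is about 0.5 to 2 points if smokers are lost more often, and about 3 to 5 points if 9% are lost and all relapse. It reaches the size of a standard error (about 7 points) only towards 25% loss with universal relapse, and that 25% may include people never treated. If abstainers are lost more often, the model is slightly too low instead.

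This does not threaten the feasibility objective or any test. It should still be corrected, because the abstinence rate from this single arm will be read as an all-treated rate.

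**What to change.** In section 7.2:

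1. Keep the MAR model and state that it covers treated participants with at least one abstinence outcome.
2. Beside it, report at each visit, and for prolonged and continuous abstinence at Weeks 13 and 26, the proportion over all participants with at least one TMS session. Count missing as smoking, and give a Wilson 95% CI and the number missing. Label it a conservative sensitivity figure.

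The cost is a few lines of text and one table column; design, sample size and visits are unchanged. The drawback is a less favourable figure that can be clearly too low when dropout is unrelated to smoking or when abstainers are lost, so it should not replace the model.

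Separately, reconcile sections 4.7.1 to 4.7.3. Section 4.7.1 treats discontinuing and withdrawing as one, 4.7.2 rules out further evaluations after withdrawal, and 4.7.3 asks for an Early Termination Visit. The text should settle whether assessments continue after treatment stops or a participant withdraws, since this decides whether someone stopped in Week 1 has any abstinence outcome.
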